### 2.1.2 Assessment battery

The cross-diagnosis and diagnosis-specific process and outcome measures used in the study are summarized in Table 1.

### 2.1.3 Strategies for data handling

**Data handling:** The Coordination Center for Clinical Trials (KKS) Dresden will be responsible for the data management according to the Good Clinical Practice Guidelines. This includes the setup of a study database by means of study software REDCap 3.3. Data will be examined by programmed range checks, validity checks, and consistency checks. REDCap is a secure web application, including an audit trail, for managing online surveys and databases. The data management will be supported by [name].-Stat. [name] and CELOS staff and resources. The responsible data officers will be jointly coordinating centrally all aspects including data handling, management and analysis in Dresden. All participating centers are intimately knowledgeable about this set-up from previous studies and have an assigned data manager, who will manage and supervise the online transmission of data and site specific quality assurance procedures. Sampling and data collection will be continuously monitored for quality by CELOS staff and the KKS Dresden. Using the KKS data management system (REDCap) established for previous clinical trials in the BMBF Psychotherapy Funding initiative the existing comprehensive internet-based data entry platform that covers all stages and components from stratified sampling to analyses will be adapted. All procedural steps and assessments will be online with automatic recall and plausibility and quality assurance measures. The assessment packages for each visit include standardized computerised diagnostic data (DIA-X CIDI). Compliance with the trial specifications, treatment integrity and compliance, and the explicit manual specifications will be monitored by random video documentation.

**Table 1.** Process and outcome measures

construct	Instrument	domain	diagnostics	baseline	intermediate	post	follow-up
			week 1	week 1	week 8	week 10	week 34
Timeline			week 1	week 1	week 8	week 10	week 34
Duration 			3 h	2 h	2h	2h	5h
primary outcomes	HAM-A / SIGH-A	somatic and psychic anxiety symptoms	X			X	X
over-arching symptomatology	DIA-X CGI BSI BDI-II ASI	categorical diagnosis symptom severity psychological symptoms depressive symptoms anxiety sensitivity	X X	X X	X X	X X	X X
diagnosis specific symptomatology	DSM-5 scales PAS ACQ BSQ	dimensional measures panic and agoraphobia agoraphobic cognitions bodily symptoms		X X X	X	X X	X X

	MI	avoidance behavior	X		X	X
	PAS	panic and agoraphobia	X		X	X
	GAD-7	worrying	X		X	X
	LSAS	social anxiety	X		X	X
impair- ment & quality of life	WHODA	quality of life	X		X	X
	S/CIDI					
	EQ5D		X		X	X
	WHO-5		X		X	X
	EMA	behavior change	X	X	X	
process variables	Sess. protocol	process exposure			after each session	
	CTS	childhood traumata	X			
	C-Scale	credibility of rationale			X	
	AAQ-II	psychological flexibility	X		X	X
	PFB-K	partnership quality	X			X
	INEP	therapeutic side effects			X	X
	STA-R	therapeutic alliance			X	X

HAM-A: Hamilton Anxiety Scale ; SIGH-A: structured interview guide for HAM-A ; CGI: Clinical Global Impression Scale ; DIA-X: Computerized Version of the Munich Composite International Diagnostic Interview (M-CIDI) ; BSI: Brief Symptom Inventory ; BDI-II: Beck Depression Inventory-II ; ASI: Anxiety Sensitivity Inventory ; DSM-5 Scales: Dimensional Anxiety Scales from the Diagnostic and Statistical Manual of Mental Disorders ; PAS: Panic and Agoraphobia Scale ; ACQ: Agoraphobic Cognitions Questionnaire ; BSQ: Body Sensations Questionnaire ; MI: Mobility Inventory ; CTS: Childhood Trauma Screener ; C-Skale: Credibility Scale ; LSAS: Liebowitz Social Anxiety Scale ; AAQ-II: Acceptance and Action Questionnaire ; PFB-K: Partnerschaftsfragebogen Kurzform ; EQ5D: EMA: Ecological Momentary Assessment; INEP: Inventar zur Erfassung Negativer Effekte von Psychotherapie ; STA-R: Skala Therapeutische Allianz-Revised ; WHO-5: WHO Well-Being Index 

## 2.2 Justification of design aspects

### 2.2.1 Controls/comparator

Given the existence of state-of-the-art exposure-based manuals with established efficacy there is no need to have an untreated control group. We thus test two variants of a highly standardized treatment manual. Both conditions are considered to be state of the art. Participants in both conditions, IPI and TAU, are expected to improve in the range of previous RCTs.

*Note: We use the acronym TAU (Treatment As Usual) for the control condition. This should not be misunderstood as meaning that TAU is the type of treatment typically applied in routine care by German providers. We refer, when using TAU to established manualized intervention programs for AD used in controlled clinical studies. Thus we provide a tough and rigorous test aiming to demonstrate that effects that are observed relate directly to modifications of extinction learning elements.*

*IPI and TAU.* Using an existing, well studied and frequently used manual template  modified for the purpose of this RCT, the manual has 12 therapy sessions (plus baseline, post, booster and FU) with identical therapeutic modules (i.e. rapport/diagnostic assessment, psychoeducation, cognitive- and behavioral exposure interventions), adapted to the type of AD and the purpose of the study. The experimental condition IPI differs only with regard to the temporal structure (higher number of trials in a shorter duration) in the behavioral exposure module in sessions 5-10, provided in only two weeks and (b) instructed spaced exposure trials during sessions 11-12. These modifications are associated with respective manualised instructions and assessment tools (see 3.3.5). In the control intervention (TAU)

this BE module will be provided over 6 weeks and no instructed spaced trials in different contexts are provided. One essential content modification in both conditions is to evoke a positive prediction error. Patients are asked for the aversive consequences that they expect to be associated with the respective standard exposure trial and about the probabilities that these consequences might occur prior, during and after exposure trials. The contingency expectancies are discussed with the patient including probability ratings for aversive consequences in subsequent exposure trials, in order to facilitate learning that the consequences did not occur at the rate expected or were not as aversive as expected. We provide this component in both groups, because we assume that the positive prediction error will specifically enhance extinction learning only in IPI.

### **2.2.2 Dose, mode and scheme of intervention**

Session 1-5 of the interventions in both groups will be identical in IPI and TAU (e.g. building up therapeutic rapport, psychoeducation, monitoring, identifying antecedents, techniques to reduce anticipatory anxiety). However, the temporal structure of sessions 5-10 and 11-12 are different, while all other sessions are identical. In the follow-up phase booster sessions participants are instructed for spaced inter-trial exposure in different contexts. Due to the study-specific requirements of documentation, assessments and quality assurance (video, patient compliance ratings etc.) each session lasts about 90 min.

### **2.2.3 Additional treatments**

Patients concomitantly treated by other psychotherapists or psychiatrists for any mental health reason are excluded. We enrol patients that prior to inclusion were on medication, but wish to stop for whatever reason after tapering out for at least 8 weeks, monitored by urine tests. In case of acute suicidality during treatment, patients will be seen by the site psychiatrists and eventually withdrawn from the trial.

### **2.2.4 Inclusion/exclusion criteria and recruitment strategy.**

To increase relevance for routine care, we intentionally keep exclusion criteria minimal. Key inclusion criteria: (1) outpatients, (2) age: 15-70 years, (3) current primary DSM-5 anxiety disorder, (4) severity at baseline (HAM-A>18) and CGI>3, (5) written informed consent, (6) able to attend on his/her own or accompanied by significant other, (7) language competence. Key exclusion criteria: (1) any DSM-IV/5 psychotic, primary mood disorders (Bipolar I, recurrent or chronic Major Depression), current Substance Dependence, (2) concomitant psychological/psychiatric treatment, (4) acute suicidality, (5) general medical contraindications, (5) mono-symptomatic Specific Phobia as the primary diagnosis.

### **2.2.5 Outcome measures**

- Consistent with all clinical trials and guidelines the primary efficacy endpoint is the clinician-rated Hamilton Anxiety Rating Scale (interview version, SIGH-A). Although the HAM-A lacks sensitivity for reflecting changes induced by psychological treatment, we are unaware of any established alternative that would work for all AD. We currently also explore the ADIS global measure of clinical severity (0-8) as an option; given this dilemma, we opted for a broader range of “secondary” outcome measures (see below).
- Other core generic outcome measures are (ordered by relevance); the Clinical Global Impression Scale (CGI), patient rated psychological (BSI) and depressive symptoms (BDI-II), anxiety sensitivity (ASI), and impairment/disability days (CIDI Harvard Index; WHODAS 2.0). The choice of these generic measures is meant to maximize comparability with other studies.

They serve as core measures to determine clinical treatment efficacy and differences between conditions in the first place. They also will be used to determine speed of recovery, being administered every 2nd session. To test diagnosis-specific effects we use as secondary endpoint(s) the DSM-5 dimensional anxiety-scales (DSM-5) and established diagnosis specific measures (i.e. PAS, ACQ, BSQ, MI, GAD-7, LSAS).

- A more reliable, objective and ecological valid evaluation of behavioral effects in everyday life is used to assess quantity, frequency and appropriateness of prescribed and natural exposure trials within sessions and between sessions. We use an innovative e-health tool that simultaneously records geographic position, mobility (actography), together with event-related momentary assessments of mood and anxiety ratings (ecological momentary assessment; EMA). Patients will be supplied with smartphones for objective assessments in real life situations.
- Subjective assessments, directly linked to experiences during standardized exposure protocol sessions, allow for (i) the quantification of subjective levels of anxiety and expectations about central concerns and (ii) the derivation of proxy measures of within- and between-session extinction, including emotional learning as well as changes in contingency expectations. Beyond the coupled experimental paradigms (P3, P4) we relate clinical outcome data to extinction learning as the central mechanism of change. For each patient an extinction curve on multiple response output measures (i.e. cognitive, autonomic) will provide information about consolidation of extinction memory, reactivation and reinstatement of fear memory as well as recall of extinction memory for each patient. These explorative proxy measures will be related to diagnostic groups and treatment outcome variables.
- To examine the impact of the intervention on the patient life and functioning we measure the generic quality of life as well as all direct and indirect health care costs (CIDI health economic module).
- In addition the CIDI, standard sets of predictors (personality, biographical and family genetic factors; baseline CAPI M-DIAX CIDI interview) are covered.

### 2.2.6 Determination of primary and secondary measures

As endpoints we use the standard total scores, derived from the respective scales (i.e. HAM-A). We explore the additional use of composite scores.

- *Monitoring:* All sites will receive regular (4) visits by study monitors to check randomly protocol adherence. Both assessment and therapy sessions will be monitored. Project violations will be documented, and lead to exclusion of patients, therapists or the center.

### **2.2.8 Proposed sample size and power calculations**

Focusing on the HAM-A total score as the core primary outcome measure for determining the sample size, we expect - building on the meta-analytic results and pilot tests - that patients in IPI group will reduce the HAM-A-score (end of treatment) by 12 points. In the TAU group we expect a reduction by 10 points. Using a power of 80%, a test significance level of  $\alpha = 5\%$ , a standard deviation of 10 points and a one-sided t-test to detect differences between the IPI and TAU group, a total of 310 patients are needed per group. Based on previous such trials  drop-out rates during treatment including follow-up of 10%-15% are expected. Total n to be enrolled is 720 and to be analyzed 620.

### **2.2.9 Compliance/Rate of loss to follow-up**

The rate of non-compliance and other drop-out has been determined based on a similar study that was just completed . The loss of 15% to follow-up is lower than in previous studies, presumably due to the treatment density.

### **2.2.10 Feasibility of recruitment**

Each center has to screen approx. 200 patients to enroll an equal number of approx. 110 patients over two years, to reach the goal of approx. 90 patients with post and follow-up for analysis (= 620 patients total). All centers have provided firm evidence to reach these targets, confirmed by the fact that such target numbers were actually exceeded in previous trials.

### **2.2.11 Stopping results**

Treatment will be discontinued on request of the patient (e.g. not willing to conduct the trials, not able to attend sessions) or in case the therapist after consulting with the supervisor comes to the decision that treatment is associated with substantial risks for the patient (i.e. need for drug treatment, suicidality). These cases will be counted as drop out. Based on the results of prior such studies as well as prior research we do not see any reason for findings that make failure criteria for the trial likely. Participating centers will be closed in case of repeated failure of recruitment or continued violation of the SOP and protocol. In this case we have two backup centers (Tübingen and Chemnitz) to replace them.

## 2.3 Statistical analyses

Statistics for the core primary outcome measure (HAM-A): In order to demonstrate that the IPI and TAU treatments differ, we use a one-tailed t-test with the following hypotheses:

$H_0: \mu_{\text{HAMADiff-IPI}} = \mu_{\text{HAMADiff-TAU}}$ ;  $H_A: \mu_{\text{HAMADiff-IPI}} > \mu_{\text{HAMADiff-TAU}}$ .

Here  $\mu_{\text{HAMADiff-IPI}}$  and  $\mu_{\text{HAMADiff-TAU}}$  are in each case the differences between the HAM-A baseline and the HAM-A value after the end of therapy in the treatment groups IPI and TAU.

Trial data will be analyzed both on an intent-to-treat (ITT) and per-protocol basis. To test whether groups have different outcomes for the major end points at (i) post and (ii) follow-up t-tests for independent samples will be used one-sided with an alpha level of 0.5. This will be also done for secondary and explorative analyses (in that case with two-sided tests). To quantify effect sizes for differences between groups at post-treatment and at follow up Cohen's d (with the pooled standard deviation at baseline in the denominator) will be used. To assess temporal changes in symptoms we will compare scores at initial assessment with those at t1 through t5. Individual outcome as a function of pretreatment characteristics will be modeled with multiple linear regression and associated analyses of variance.

Data will be analyzed with STATA and, if necessary, statistical weights will be used to adjust for different sampling probabilities in different study centers. LOCF-analyses (intent-to-treat) will be carried out as well as completer analyses and mixed models (saturated for the combined effects of time and group on outcome) to assess whether dropout changes the conclusions. Moderator analyses (predictors of treatment effects within IPI and TAU patients) will address type, respectively group of disorders as well comorbidity using dimensional and categorical measures. Pearson correlations between such comorbidity measures and outcome will be calculated. Associations with categorical predictors will be analyzed with linear regressions using dummy variables and quantified with mean differences in treatment outcome (and their 95% confidence intervals).

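### The primary HAM-A change-score t-test is valid but fixes the baseline slope at 1 and leaves centre to a data-dependent rule; a prespecified baseline-adjusted model would be at least as precise in large samples.

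*Combined protocol and SAP*

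**What the plan says.** Section 2.3 introduces the primary test with "In order to demonstrate that the IPI and TAU treatments differ, we use a one-tailed t-test with the following hypotheses" and defines the quantities compared, which "are in each case the differences between the HAM-A baseline and the HAM-A value after the end of therapy". No covariate is named for this test.

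Other models appear in the same section, each with its own purpose:
- The mixed models are "mixed models (saturated for the combined effects of time and group on outcome) to assess whether dropout changes the conclusions". They contain time and group, and they are a check on dropout.
- A regression has this aim: "Individual outcome as a function of pretreatment characteristics will be modeled with multiple linear regression and associated analyses of variance". The text does not say whether arm is in the model, and does not present it as the treatment test.
- The moderator analyses look for predictors within each arm.
- Centre appears only through weights: "if necessary, statistical weights will be used to adjust for different sampling probabilities in different study centers".

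Section 2.2.7 sees no need to consider prognostic factors at randomisation, because recruitment is stratified. It adds that centre effects are unlikely and will be controlled if they arise (reading the printed word 'side' as 'site'). It gives neither the trigger nor the model.

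Section 2.2.8 plans with "a standard deviation of 10 points and a one-sided t-test to detect differences between the IPI and TAU group" and concludes that "a total of 310 patients are needed per group". It does not say whether the SD is that of change or of a raw score. Baseline HAM-A is known for every patient, because entry requires "severity at baseline (HAM-A>18) and CGI>3".

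**The concern.** A t-test on change is the same as regressing post score on arm with the baseline coefficient set to 1. If the true slope differs from 1, part of the baseline variation stays in the error term and precision already paid for goes unused. The margin is thin: the design targets a 2-point difference between two active treatments and reaches its 80% power with nothing to spare.

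The conditional centre rule is a second, smaller matter. If centre enters the model only when an effect is seen, the final primary model is not fixed until the data are in. Stratified recruitment does not remove the reason to adjust, since it governs who enters the trial and does not by itself balance the arms. Diagnosis is a weaker candidate than baseline or centre: section 1.2 mentions generalised anxiety disorder as a possible exception with slightly poorer results, yet expects similar outcomes across diagnoses.

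**Working it through.** **Inputs from the documents.** Mean reductions of 12 and 10 points (difference 2), SD 10, one-sided 5%, 310 per group (section 2.2.8); 720 enrolled and 620 analysed; 7 centres and 6 diagnoses (section 0); two backup centres (section 2.2.11). The 1:1 allocation is inferred from the equal group sizes. Section 2.3 prints alpha as 0.5; the 5% of section 2.2.8 is used here because only that value reproduces 310.

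**Assumed.** r = pre-post correlation, 0.3 to 0.7. k = baseline SD / post SD, 0.5 to 0.7, taken as plausible because the entry cut-off narrows the baseline spread. The documents give neither.

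**1. The plan's own figure.** Power = Φ(2 / (SD × √(2/310)) − 1.645). With SD 10 the standard error is 0.803, so power = Φ(2.490 − 1.645) = 80.1%. The stated 310 reproduces.

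**2. Variances, in units of post-score variance.**
- Change score: 1 + k² − 2rk
- Baseline-adjusted: 1 − r²
- Difference: (k − r)², never negative, and zero only if k = r, that is, slope r/k = 1.

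At 1:1 the large-sample ordering also holds when slopes differ between arms.

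**3. If SD 10 is the SD of change** (unadjusted power 80.1%):

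| k | r | slope | variance ratio | adjusted power |
|---|---|---|---|---|
| 0.7 | 0.3 | 0.43 | 0.910/1.070 = 0.850 | 85.4% |
| 0.7 | 0.5 | 0.71 | 0.750/0.790 = 0.949 | 81.9% |
| 0.7 | 0.7 | 1.00 | 0.510/0.510 = 1.000 | 80.1% |
| 0.5 | 0.3 | 0.60 | 0.910/0.950 = 0.958 | 81.6% |
| 0.5 | 0.5 | 1.00 | 0.750/0.750 = 1.000 | 80.1% |
| 0.5 | 0.7 | 1.40 | 0.510/0.550 = 0.927 | 82.7% |

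The gain is 0 to 5.3 points.

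**4. If SD 10 is the post-score SD** (change-score versus adjusted power at r = 0.3 / 0.5 / 0.7):
- k = 0.7: 77.7 vs 83.3%, 87.6 vs 89.1%, 96.7 vs 96.7%
- k = 0.5: 81.9 vs 83.3%, 89.1 vs 89.1%, 95.7 vs 96.7%

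The gain is 0 to 5.6 points.

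**5. Intent-to-treat with last observation carried forward.** Assume 720 randomised, p = 100/720 = 13.9% lost before the post assessment equally in both arms, baseline carried forward for them (zero change), and change SD 10 in the rest.
- Difference: (1 − p) × 2 = 1.722.
- Change variance in an arm with mean change m: (1 − p) × 100 + p(1 − p)m², which is 103.3 for m = 12 and 98.1 for m = 10, average 100.7.
- Unadjusted power: Φ(1.722 / √(2 × 100.7/360) − 1.645) = 74.5%.
- Adjusted: the slope becomes B = (1 − p)(r/k) + p. For k = 0.7, r = 0.3, B = 0.508, the average residual variance is 89.6 and power is 78.7%. Over the six (k, r) pairs of step 3, adjusted power runs from 74.5% to 78.7%.

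The gain is 0 to about 4 points.

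**6. Cost if nothing is prognostic and k = r.** Baseline 1 + centres 6 + diagnoses up to 5 = 12 degrees of freedom. Variance inflation is about 1 + 12/605 = 1.0198, and power 79.4%. With both backup centres there are 14 degrees of freedom, and power is 79.3%. The 12 degrees of freedom are recovered once the covariates explain 1 − 1/1.0198 = 1.9% of residual variance. A simulation of 6,000 runs at k = r = 0.5 gave 79.5% for the t-test and 78.6% with all covariates, a gap of 0.9 points. Error under the null stayed between 4.5% and 5.4%.

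**The case against.** The strongest reply is that nothing here is an error. The planned test matches the one used for sample size, reaches its stated power and is unbiased under randomisation. The possible gain includes zero. All of that stands: the point concerns efficiency and prespecification only.

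Some stronger readings are tempting, and the documents do not support them:
- **Power of 85% to 93%, or 201 to 263 patients per arm.** These figures require equal SDs at baseline and post (k = 1.0) with r of 0.3 to 0.7. The entry cut-off makes that doubtful. Moreover r and k are not independent: truncating the baseline lowers both, so not every cell of the table is equally credible.
- **Randomisation is stratified by diagnosis and the test ignores it.** The sample-size entry of section 0 speaks of stratified allocation to the trial, not to arm. Its entry on eligibility refers to stratified sampling, and section 2.2.7 to stratified recruitment. Together they point mostly to stratified entry. A clarifying sentence is needed, but no contradiction is shown.
- **A hard ceiling of 0.7 points on the cost.** The loss from 80.1% to 79.4% holds for 12 degrees of freedom. Backup centres take it slightly further, so 'under about 1 point' is the safer statement.

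A reader might instead think that the planned mixed model already adjusts for baseline. With complete data, its group-by-time contrast at post equals the change-score difference, so it does not.

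**Conclusion.** The point holds as a recommended improvement, with medium confidence. The primary test is valid, but it fixes a slope that could be estimated from data in hand, and it leaves the handling of centre open. Baseline adjustment targets the same mean difference and, in large samples at 1:1, cannot be less precise.

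The size is modest and rests on assumed r and k: 0 to about 5 or 6 power points among 620 analysed patients, depending on what the SD of 10 describes, and about 0 to 4 points in the carried-forward set. The absence of a diagnosis term and the unclear meaning of the SD are clarity points, not faults in the test.

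**What to change.** In section 2.3, prespecify the primary analysis as a linear model of post HAM-A on arm, with baseline HAM-A as a covariate and centre as a fixed factor. The centre term replaces the conditional rule in section 2.2.7. Keep the change-score t-test as a sensitivity analysis, and treat the centre sampling weights the same way, since they serve a different purpose.

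Primary diagnosis group may be added if its categories are defined beforehand. It must be included if randomisation to arm is in fact stratified by diagnosis, so section 0 and section 2.2.7 should say plainly whether it is. Section 2.2.8 should state whether the SD of 10 is that of change.

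The cost is plan wording and a slightly larger model. Baseline HAM-A, centre and diagnosis are already collected, so no patients or visits are added. If none of the covariates is prognostic, the loss is under about 1 power point.

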## 0. Summary

APPLICANT/ COORDINA- TING INVE- STIGATORS	[name]. [name] & [name]. [name] (Co-PI) Institute of Clinical Psychology and Psychotherapy & CELOS Technische Universität Dresden [name] [contact]; [contact] [contact]
TITLE	Optimizing Extinction Using Intensified Psychological Interventions (IPI) for Adult Anxiety Disorders (AD)
CONDITION	DSM-5: Panic Dis. (PD), Generalized Anxiety Dis. (GAD), Agoraphobia (AG), Social Anxiety Disorder (SAD), Specific Phobias (SP), Separation Anxiety Dis.(SepAD), and associated comorbid conditions
OBJECTIVE	To examine the efficacy of intensified psychological interventions (IPI) aiming to augment extinction learning during exposure. In IPI we increase the number of exposure trials and decrease the spacing between sessions providing more “extinction trials” over a shorter duration. To stabilize treatment effects we provide spaced exposure training during follow-up (booster) in different contexts. We also based exposure on a positive prediction error model. We hypothesize that IPI results in stronger, faster and more pervasive effects in subjective, behavioural, physiological, neural and epigenetic indices at post and follow-up via optimizing extinction learning. To test the hypothesis, we propose a multicentre randomized clinical trial (RCT). Patients will be randomly allocated to either IPI or standard research exposure treatment as usual (TAU) as the control condition. Primary hypotheses: (1) IPI will be superior to TAU at post and follow-up on primary and secondary outcome measures and will recover faster. Secondary hypotheses are: (2) IPI is associated with enhanced positive prediction error to increase extinction learning during and after exposure and (3) will result in more pronounced changes in behavioural proxy measures (between session reduction of fear, anxiety, avoidance) of extinction learning. We also explore the effect of type of diagnosis and comorbidity as potential moderators of outcome and extinction. We further expect that IPI will be associated with lower direct and indirect health care costs.

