OUTCOME(S)	
Primary efficacy endpoint is the clinician-rated Hamilton anxiety score (SIGH-A). Key secondary endpoint(s): CGI total score, patient rated generic (BSI) and diagnosis-specific symptom scores (i.e. FFS, PAS, MI), impairment/disability days (CIDI Harvard Index, SDS), depression (dimensional: BDI, categorical: CIDI) quality of life (EQ-5D) and social functioning (SAS). As an objective and ecological valid measure for exposure trials we use a novel combined mobile mobility-EMS tool (see proposal ESPRIT). The range of measures is meant to demonstrate that IPI is associated with more pervasive changes in various domains. As proxy measure for extinction learning we use subjective measures of within-session and between-session exposure effects (anxiety ratings, expectancy ratings of central concerns). (Note: see further assessments in P3-P6.)
 
Assessment of safety: suicidality assessment and adverse behavioural effects.

STUDY TYPE	Randomised controlled clinical trial with two active conditions associated with mediator and moderator analyses (see projects P3-6)
STATISTICAL ANALYSES	
Efficacy: HAMA total score (standardized interview, SIGH-A)
 
Description of primary efficacy: Superiority of IPI against TAU will be tested with t-tests for independent samples using an alpha level of 0.5. Intent-to-treat (ITT), completer analyses will be conducted and mixed models (saturated for the joint effects of treatment group and time) fit to address dropout.
 
Safety: N/A
 
Secondary endpoints: ITT, completer analysis and mixed models as above but with two-sided tests in case of explorative analyses. Pearson correlations between dimensional comorbidity measures and outcomes will be calculated, Associations with categorical predictors will be analyzed with linear regressions.

SAMPLE SIZE	
To be assessed for eligibility n=1.400
 
To be allocated in a stratified way (by diagnosis) to trial (n = 720)
 
To be analysed (n = 620)

TRIAL DURATION	
First patient in: 6/1st year – last patient out (fup): 1/4th year
 
Recruitment and enrolment: start: 6/1st year
 
Duration of the entire trial: 36 months
 
Recruitment period: 6/1st year – 5/3rd year

CENTERS	7: Greifswald, Berlin, Münster, Marburg, Dresden, Bochum, Würzburg

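### The plan does not say which test decides primary hypothesis 1: it covers two time points and several measures without multiplicity control, while the 80% power is for HAM-A at end of treatment only

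*Combined protocol and SAP*

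**What the plan says.** The Summary (Objective) labels as primary the hypothesis that "IPI will be superior to TAU at post and follow-up on primary and secondary outcome measures and will recover faster". Its Outcome row names HAM-A (SIGH-A) as the primary efficacy endpoint without a time point and lists CGI, BSI, BDI, disability days and others as key secondary.

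Section 2.2.8 sizes the trial on one comparison. It expects "that patients in IPI group will reduce the HAM-A-score (end of treatment) by 12 points" against 10 points under TAU, with SD 10, a one-sided 5% t-test, 80% power and 310 patients per group.

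Section 2.3 opens with one formal one-tailed hypothesis on HAM-A, where the quantities compared are "in each case the differences between the HAM-A baseline and the HAM-A value after the end of therapy". The next paragraph widens this to two times: "groups have different outcomes for the major end points at (i) post and (ii) follow-up t-tests for independent samples will be used one-sided". The alpha printed there is 0.5 ("will be used one-sided with an alpha level of 0.5"), as it is in the Summary.

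On secondary measures, section 2.3 specifies two-sided tests for secondary and explorative analyses, whereas the Summary mentions two-sided tests only for explorative ones. Section 2.2.5 lists CGI, BSI, BDI-II, ASI and disability by relevance and then says of the generic measures: "They serve as core measures to determine clinical treatment efficacy and differences between conditions in the first place". A multiplicity correction is mentioned only for the (epi)genetics add-on (section 5.4).

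**The concern.** A hypothesis labelled primary that spans two time points and several measures needs a rule for when it counts as confirmed. None is given for the RCT. A win at post only, at follow-up only, or on CGI or BSI without HAM-A could each be presented as support for it.

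The two natural readings have different consequences. If any one success is enough, the error rate is above the level of each test. If success is needed at both times, the 80% in section 2.2.8 is not the power of the claim.

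The time points could well disagree. Section 1.1 reports that massed exposure may speed extinction at the price of more return of fear, and that spaced exposure tends to help in the long term. The rule should be fixed before the data are seen.

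**Working it through.** **Inputs from the documents.** Difference 12 − 10 = 2 points, SD 10, 310 per group, one-sided 5% (section 2.2.8); two time points for the major end points (section 2.3). **Assumed.** The correlation ρ between the post and follow-up test statistics, which the documents do not give (0 to 0.9 shown), and, unless stated otherwise, a follow-up difference that is also 2 points.

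**Step 1: reproduce the plan's figure.** n per group = 2(z₀.₉₅ + z₀.₈₀)² SD²/Δ² = 2(1.645 + 0.842)² × 100/4 ≈ 309.1, rounded up to 310. In reverse, the expected test statistic is λ = 2/(10√(2/310)) = 2.490, so power = Φ(2.490 − 1.645) = Φ(0.845) = 80.1% (80.0% with the noncentral t). The sample size is correct for one test of HAM-A at end of treatment.

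**Step 2: two HAM-A tests, each at one-sided 5%.**
- Either counts: chance of at least one false win = 1 − Φ₂(1.645, 1.645; ρ).
- Both must win: power = Φ₂(0.845, 0.845; ρ).

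| ρ | At least one false win | Power to win both |
|---|---|---|
| 0 | 9.75% | 64.2% |
| 0.3 | 9.3% | 66.8% |
| 0.5 | 8.8% | 68.8% |
| 0.7 | 8.0% | 71.4% |
| 0.8 | 7.5% | 73.0% |
| 0.9 | 6.8% | 75.1% |

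If the follow-up difference were 1.5 points (an assumption for sensitivity only), the second argument becomes 0.75 × 2.490 − 1.645 = 0.222, and joint power is about 47% to 58% over the same range. To reach 80% for winning both with 2 points at each time would take 420, 396 or 380 per group at ρ = 0, 0.5 or 0.7.

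**Step 3: add the secondary measures.** Take six core measures (HAM-A, CGI, BSI, BDI-II, ASI, disability) at two times, 12 tests in all. Following section 2.3, the 2 HAM-A tests are one-sided at 5% and the 10 secondary tests two-sided at 5%, so a secondary test favours IPI falsely if Z > 1.960. Simulation with one common assumed correlation (400,000 draws) gives a chance of at least one false IPI-favouring result of about 23%, 18% and 14% at correlation 0.3, 0.5 and 0.7.

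**Step 4: a fixed sequence.** Test HAM-A at post at one-sided 5%, and HAM-A at follow-up at the same level only after a success. If there is no true post effect, any false claim requires a false win at post, which has probability at most 5%. If there is one, the only possible HAM-A error is at follow-up, again at most 5%. Power for post stays at 80%, and power to win both is the right-hand column above.

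**The printed alpha.** Read literally, 0.5 would give each test a 50% error rate. The figures above use the 5% of section 2.2.8, which is the value that reproduces 310.

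**The case against.** The strongest reply is that section 2.3 opens with a single formal HAM-A hypothesis at end of therapy, section 2.2.8 sizes exactly that test, and the Summary names one primary endpoint. If that test alone decides, the level is 5% and the power 80%. This stands as a possible reading, so it would be wrong to conclude that either the error rate must exceed 5% or the power must fall below 80%. But no sentence gives that test sole authority, and the hypothesis labelled primary says otherwise.

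Taken literally, that hypothesis joins post **and** follow-up. If both are required, the false-claim rate is at most 5% and only power suffers. That also stands.

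A reader might infer three stronger things that the documents do not support:
- **That every secondary measure is tested one-sided at the full level.** The 12-test figures would then be about 34%, 27% and 20%. Section 2.3 makes secondary tests two-sided; the Summary is merely ambiguous.
- **That follow-up is the only time at which the whole IPI package is evaluated.** Sections 2.1.2 (Treatment description) and 2.2.1 place spaced exposure for IPI in sessions 11-12, and section 5.3 puts the post assessment after session 12. The Summary places spaced trials in the booster and follow-up period. The passages disagree, so the inference is unsafe.
- **That secondary status is undefined.** The Summary already lists most of these measures as key secondary, and section 2.2.5 ranks them. What is missing is how that ranking enters the testing.

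Finally, an intent-to-treat analysis with LOCF could use all 720 allocated. At 360 per arm with an undiluted 2-point effect, λ = 2/(10√(2/360)) = 2.683, and joint power is 74% to 79% for ρ from 0.3 to 0.8. That is optimistic about dropouts, and it is not the basis on which section 2.2.8 states its power.

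**Conclusion.** The point holds as a missing decision rule with measurable consequences. The plan states one primary hypothesis over two times and several measures, prescribes tests of the major end points at both times at the same level, and justifies the sample size for one of them. At 5% per test, the HAM-A claim has an error rate of 6.8% to 9.75% if either time suffices, or about 64% to 75% power at 310 per arm if both are needed. Counting the core secondary measures raises the chance of some false IPI-favouring result to about 14% to 23%.

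The direction of the first result holds at every correlation shown; the exact sizes depend on correlations that the documents do not give. The power range also assumes that the 2-point difference persists to follow-up. The 12-test figure further depends on counting six measures and on a common correlation.

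**What to change.** - **Summary (Objective) and section 2.3:** name HAM-A change from baseline to post as the single confirmatory test, as sized in section 2.2.8. Test HAM-A at follow-up at the same one-sided level only if the post test succeeds.
- **Same places:** treat CGI, BSI, BDI-II, ASI and disability as secondary. Either test them after that, in the order of section 2.2.5 and stopping at the first failure, or report them without a confirmatory claim.
- **Summary and section 2.3:** state one sidedness for the secondary tests and correct the alpha from 0.5 to 0.05.
- **Section 2.2.8:** say that 80% power refers to the post test alone, and that winning at both times has about 64% to 75% under the stated assumptions.

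The change is wording only and adds no patients or visits. It has two costs. A benefit that appears only at follow-up could not be claimed as confirmatory, and the power stated for the joint claim becomes less favourable. If the sponsor wants follow-up to stand on its own, splitting alpha is an alternative, at a price: at one-sided 2.5% each, power per test at 310 per group is 70.2%, and 80% would need 393 per group.
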